### 7.6.1 Required Concomitant Treatment

#### 7.6.1.1 Loperamide Antidiarrheal Therapy

Diarrhea is the major dose-limiting toxicity of neratinib with onset typically occurring early in the course of treatment (during the first few weeks). Primary prophylactic use of antidiarrheal medication is **mandatory** for all enrolled patients in the neratinib study.

Loperamide is the recommended standard therapy to treat diarrhea in this study. If alternative antidiarrheal medication is proposed, this should be discussed with the PI and the reason documented in the source documents. Second-line antidiarrheal treatments and adjunctive

therapies (i.e., octreotide [SANDOSTATIN®]) (or equivalent as approved by the PI) are also recommended for use when appropriate.

All patients are required to receive intensive diarrhea prophylaxis:

- For the first 14 days, loperamide 4 mg (2 tablets/capsules) will be self-administered orally by patients 3 times a day (total 12 mg a day). The initial dose of loperamide 4 mg will be self-administered orally with the first dose of neratinib.
- After the first 14 days, loperamide 4 mg (2 tablets/capsules) will be self-administered orally twice a day (total 8 mg a day) through the first cycle of therapy (Day 28) from start of neratinib dosing.
- Thereafter, loperamide will be administered as needed (not to exceed 16 mg per day). The goal is to titrate to 1-2 bowel movements a day. Recommended loperamide dosing is listed below in **Table 5**.

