**Table 5: Loperamide Dosing**

Day	Loperamide Dose
1	4mg at time of first dose of neratinib, then 12mg in 3 divided dose of 4mg tid
2-14	Daily dose of 12 mg in 3 divided doses of 4 mg tid
15-28	Daily dose of 8 mg in 2 divided doses of 4 mg bid
29+	Daily dose as needed (not to exceed 16 mg per day)

Patients must use a diary to record intake of loperamide. Loperamide pill counts will be conducted during the first 2 cycles (56 days) of therapy.

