#### **Loperamide Dose Adjustment:**

Patients are expected to take loperamide prophylaxis as directed. However, patients may require individualization of loperamide prophylaxis dose (up to a maximum dose of 16mg per day) with the goal of titrating to 1-2 bowel movements a day.

- For patients who develop diarrhea during Cycles 1-2, loperamide should be increased up to a maximum of 16 mg a day.
- If a patient is unable to tolerate loperamide due to symptomatic constipation, loperamide should be held until after the first bowel movement and then resumed at a dose reduced by one level.
- For recurrent symptomatic constipation events, hold loperamide until after the first bowel movement and then resume at a dose reduced to the next lower dose level.
- If a patient is unable to tolerate once-daily loperamide due to constipation, hold loperamide and discuss subsequent loperamide dosing with the Medical Monitor.
- Neratinib dosing should continue if loperamide is held.

Recommended dose reductions for the -1 and -2 dose levels of loperamide are listed in **Table 6**.

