### Monitoring and Personnel Responsible for Monitoring

The Protocol Management Team (PMT) is responsible for monitoring the data and safety of this study. The PMT consists of the Principal Investigator (PI), Collaborating Investigator, CRA/protocol nurse, and Biostatistician. The PMT is responsible for monitoring the data and safety of this study, including implementation of the stopping rules for safety and efficacy.

The PMT is required to submit periodic status reports (i.e., the PMT Report) according to the frequency prescribed in the [City of Hope Institutional Data and Safety Monitoring Plan](#) [policy dated 07/09/2014]. Important decisions made during PMT meetings only need to be noted in the PMT Report submitted to the Data and Safety Monitoring Committee (DSMC).

Protocol specific data collection will include the following items:

After 20 patients have completed one full cycle of therapy, the study team will review the data and assess the toxicity profile and rates of dose reduction, delays, interruptions and hospitalization related to the agent. Within this interim analysis, a specific review will be made of the data for the patients over 75 years of age. Additional guidelines will be used to flag an unexpected number of patients that experience symptomatic cardiac toxicity (NYHA Class III or

IV if cardiac failure, or Grade 3 or higher by NCI NCTAE v4.0 for other cardiac events), safety of neratinib in older adults (using CRFs based on CTCAE v.4.0), efficacy of neratinib in older adults (based on imaging using RECIST 1.1 criteria), geriatric assessment of older adults, adherence of the population to the oral medication, or cardiac safety in the study population (using cardiac imaging).

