#### **15.2.2 Stopping Rules (see Table 17)**

As diarrhea has been seen with neratinib, we have established additional guidelines and criteria which will be used to flag an unexpected number of patients that experience grade 3 diarrhea within the 2 cycles on neratinib treatment in the presence of aggressive mandatory anti-diarrhea management.

The risk set to be used in the safety monitoring decision (to trigger a review of the protocol) will include all patients that have received the neratinib in the presence of aggressive mandatory anti-diarrhea management.

Every time a patient experience  $\geq$  grade 3 diarrhea within the first 2 cycles on treatment in the presence of aggressive mandatory anti-diarrhea management we will look at the column for the total number of patients that have experienced this toxicity (X), and compare the total number of patients, N, who are in the risk set to Nx. If the total number of patients, N, is greater than Nx, the number given in the bottom row of the table below, then accrual will continue. If N is less than or equal to Nx, then the monitoring boundary will have been crossed and a careful review of the trial data will be mandated.

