**Table 17: Criteria for Suspending Accrual to Evaluate Safety**

X: # pts who experience $\geq$ grade 3 diarrhea within the first 2 cycles on neratinib treatment in the presence of aggressive mandatory anti-diarrhea management.	4	5	6	7	8	9	10	11	12
Nx: safety boundary crossed if # patients in risk set (N) is less than or equal to Nx (if $N \leq Nx$ )	$\leq 6$	$\leq 11$	$\leq 16$	$\leq 20$	$\leq 25$	$\leq 29$	$\leq 34$	$\leq 38$	$\leq 40$

These rules were selected to ensure a low probability that the safety boundary would be crossed, indicating excessive  $\geq$ grade 3 diarrhea, if the true chance of  $\geq$ grade 3 diarrhea were less than 15% and a high probability that the boundary would be crossed if the true chance of  $\geq$ grade 3 diarrhea reached 30%. Criteria for flagging an excessive number of patients that have toxicity are based on the sequential probability ratio test with  $a=0.10$ ,  $b=0.10$ ,  $po=0.15$  and  $pa=0.30$ . The table below summarizes these probabilities. The values in **Table 18** below are based on 10,000 simulations.

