#### Medications to treat diarrhea

My study doctor/team will provide me with loperamide on day 1 with the instruction to start treatment with loperamide along with the first dose of neratinib. I need to take the medications as directed by my study doctor/team.

Loperamide:

- I will initially take 2 tablets/capsules (4 mg) with the first dose of neratinib
- Thereafter, I will take 2 tablet/capsule (4 mg) three times a day for the next two weeks; if I get constipated, I should contact my study doctor/team who will instruct me on how often and how much loperamide to take but I should not stop taking loperamide.
- After the first two weeks, I will take 2 tablet (4 mg) twice a day onwards through the first 1cycle of therapy (28days) from the start of neratinib regardless of whether I have diarrhea or not.
- If I continue to have diarrhea while taking loperamide, I should contact my study doctor/team for additional anti-diarrheal medication and consult.
- If I have diarrhea with increase of up to 6 stools per day over usual any time after completing the two cycles of therapy and I am not taking any anti-diarrheal medication, I will take 2 tablets/capsules (4 mg) immediately after the first loose stool and then 1 tablet (2 mg) every 4 hours or after each loose stool to a maximum dose of 8 tablets/capsules (16 mg) in any 24 hour period until I haven't had any loose stool for at least 12 hours.

Other medication (Study doctor/team to write in name of medication and instructions):

---

---

---

In case of more severe diarrhea and any diarrhea associated with fever, pain, infection, or dehydration, I may receive IV fluids, antibiotics and/or other medications

---

---

---

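### Does the diarrhea stopping boundary leave open which events count after mandatory prophylaxis ends at Day 28?

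*Combined protocol and SAP*

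**What the plan says.** Section 15.2.2 sets a sequential boundary for grade 3 or higher diarrhea. At each event "within the first 2 cycles on treatment in the presence of aggressive mandatory anti-diarrhea management we will look at the column" for X, the number of patients affected so far, and compare the risk set N with the limit Nx. The risk set "will include all patients that have received the neratinib in the presence of aggressive mandatory anti-diarrhea management". If N is at or below Nx, a review of the trial data is required. The text under Table 17 wants a low chance of crossing below a 15% rate and "a high probability that the boundary would be crossed if the true chance of" grade 3 or higher diarrhea reached 30%.

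Section 7.6.1.1 makes prophylaxis compulsory for all patients, with scheduled loperamide continuing "through the first cycle of therapy (Day 28) from start of neratinib dosing". Table 5 then gives, from Day 29, "Daily dose as needed (not to exceed 16 mg per day"). Under Loperamide Dose Adjustment, loperamide may be stopped for symptomatic constipation, and "Neratinib dosing should continue if loperamide is held". The patient instructions in Appendix K speak of diarrhea "any time after completing the two cycles of therapy and I am not taking any anti-diarrheal medication". Section 9.0 gives the Protocol Management Team responsibility for monitoring, "including implementation of the stopping rules for safety and efficacy".

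**The concern.** The phrase about aggressive mandatory management qualifies both X and N, and Section 15.2.2 does not define it. In Section 7.6.1.1 the word mandatory is attached to primary prophylaxis, whose fixed schedule covers only the first 28 of the 56 days in the window. A strict reader could say that an event on Day 35, or one during a loperamide hold, did not occur under mandatory management and so does not enter X. The patient would still be in N, having received neratinib under the plan, and the boundary would become harder to cross.

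One event can matter. Six events among 16 patients cross the boundary (for X = 6, Nx = 16). Leave one out and five among 16 do not (for X = 5, Nx = 11). The Protocol Management Team, which includes the principal investigator, applies the rule in an open-label trial, and this is the only trigger in the plan with a numeric threshold. At stake is whether the boundary has the sensitivity that Table 18 claims.

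**Working it through.** **Inputs.** From Section 15.2.2: sequential probability ratio test with a = b = 0.10, p0 = 0.15, pa = 0.30; Nx = 6, 11, 16, 20, 25, 29, 34, 38, 40 for X = 4 to 12. From Section 15.1: at most 40 patients.

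**Step 1: reproduce Table 17.** The upper boundary is

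Nx = floor{ x + [x·ln(pa/p0) − ln((1−b)/a)] / [−ln((1−pa)/(1−p0))] }

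with ln(0.30/0.15) = 0.6931, ln(0.90/0.10) = 2.1972 and −ln(0.70/0.85) = 0.1942. For x = 4: 4 + (2.7726 − 2.1972)/0.1942 = 6.96, so 6. For x = 6: 6 + (4.1589 − 2.1972)/0.1942 = 16.10, so 16. For x = 12 the value is 43.5, capped at 40. All nine limits match.

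**Step 2: reproduce Table 18.** Exact recursion over patients 1 to 40, with every event counted, outcomes known at once and the boundary checked at each event:

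| True rate | Exact | Table 18 |
|---|---|---|
| 5% | 0.0003 | <0.001 |
| 15% | 0.061 | 0.07 |
| 30% | 0.714 | 0.71 |
| 50% | 0.9987 | >.99 |

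The largest gap is about one percentage point. Table 18 therefore describes a rule that counts every event.

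**Step 3: what the narrow reading would cost.** Let a share s of events be left out of X while those patients stay in N. The counted rate is p(1 − s) and the boundary is unchanged. The documents give no value for s, so a range is assumed.

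| s | Crossing at true 30% | Crossing at true 15% | Opposite decisions from the two counts, true 30% |
|---|---|---|---|
| 0 | 0.714 | 0.061 | 0 |
| 5% | 0.645 | 0.047 | 6.9% |
| 10% | 0.570 | 0.036 | 14.4% |
| 20% | 0.411 | 0.020 | 30.3% |
| 30% | 0.260 | 0.010 | 45.4% |

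Section 7.6.1.1 places onset in the first few weeks. If onset is exponential truncated at 56 days with mean parameter m, the share after Day 28 is e^(−28/m)/(1 + e^(−28/m)): about 6%, 12% and 20% for m = 10, 14 and 20 days (assumed). The 30% row lies beyond that range. Simulated with entry at 1.5 patients per month, crossing at a true 30% is about 0.70 when all events count, against about 0.62, 0.53 and 0.40 when only events to Day 28 count.

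**Step 4: which reading the text supports.**

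- The rule speaks of management, not of scheduled prophylaxis. Section 7.6.1, headed Required Concomitant Treatment, includes loperamide increases for diarrhea in Cycles 1–2, a plan for Cycle 2 onward (7.6.1.3) and management of complicated grade 3 diarrhea (7.6.1.4). As-needed dosing and holds for constipation are themselves part of it.
- Loperamide pill counts run for 56 days and diary review for two cycles. Both match the window in Section 15.2.2.
- If management ended at Day 28, stating a two-cycle window in the text and in both tables would serve no purpose.
- X and N carry the same qualifier. The mismatch needs it read per event for X and per patient for N. Read per patient for both, with prophylaxis required of everyone, N is all treated patients and X is those among them with an event by Day 56.
- Section 1.4.5.5 reports 12–16% severe diarrhea with prophylaxis and 28–39% without. These sit near p0 and pa, which suggests that the phrase describes the regimen under which the rates are judged rather than filtering single events.

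**The case for a change.** The strongest reply is that the broad reading is nowhere written down. Mandatory is the word Section 7.6.1.1 uses for prophylaxis, and Section 10.2.1 links the intensive plan to the first cycle. Nearby text is untidy: one list refers to diarrhea in Cycles 1–2 where a similar one in 7.6.1.2 refers to Cycle 1, and Appendix K prescribes loperamide through one cycle and then mentions completing two. A safety trigger should not rest on inference when two sentences would settle it, and those sentences would need no new data or patients.

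Part of this stands. The qualifier is undefined in Section 15.2.2, and an explicit line would be better drafting. It does not follow that X is undefined: grade, window, unit and risk set are all stated. The suggested wording would give the same count that the ordinary reading gives, with both tables untouched. That the team would choose case by case near the boundary is conjecture. A missed crossing would also not leave toxicity unseen, because Section 15.2.1 has a review after 20 patients covering all grades of gastrointestinal toxicity, and Section 9.0 requires periodic reports.

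**Conclusion.** No change to the plan follows. This is a gap in wording that analysts would fill sensibly by counting every treated patient with grade 3 or higher diarrhea in the first two cycles, whatever anti-diarrheal was being taken at onset. On that count the rule has the properties Table 18 states: 0.061 at 15% and 0.714 at 30% by exact calculation, against 0.07 and 0.71.

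The losses in Step 3 (0.714 down to between 0.645 and 0.260) require both the strained reading and an excluded share that the documents do not supply. On the ordinary reading the loss is zero. The conclusion rests on Section 7.6.1 as a whole being the management that Section 15.2.2 refers to, which the 56-day pill counts and the two-cycle window support.

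Two drafting matters are separate and do not bear on the boundary. The rule's introductory sentences say grade 3 where the operative text says grade 3 or higher, and Section 7.6.1.1, Table 5 and Appendix K should be reconciled on the duration of prophylaxis. This review takes no position on that duration.

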**Table 17: Criteria for Suspending Accrual to Evaluate Safety**

X: # pts who experience $\geq$ grade 3 diarrhea within the first 2 cycles on neratinib treatment in the presence of aggressive mandatory anti-diarrhea management.	4	5	6	7	8	9	10	11	12
Nx: safety boundary crossed if # patients in risk set (N) is less than or equal to Nx (if $N \leq Nx$ )	$\leq 6$	$\leq 11$	$\leq 16$	$\leq 20$	$\leq 25$	$\leq 29$	$\leq 34$	$\leq 38$	$\leq 40$

These rules were selected to ensure a low probability that the safety boundary would be crossed, indicating excessive  $\geq$ grade 3 diarrhea, if the true chance of  $\geq$ grade 3 diarrhea were less than 15% and a high probability that the boundary would be crossed if the true chance of  $\geq$ grade 3 diarrhea reached 30%. Criteria for flagging an excessive number of patients that have toxicity are based on the sequential probability ratio test with  $a=0.10$ ,  $b=0.10$ ,  $po=0.15$  and  $pa=0.30$ . The table below summarizes these probabilities. The values in **Table 18** below are based on 10,000 simulations.

**Table 18: Probability of Crossing the Safety Boundary (i.e. too many patients have TOX)**

True Chance of Experiencing experience $\geq$ grade 3 diarrhea within the first 2 cycles on neratinib treatment in the presence of aggressive mandatory anti-diarrhea management.	5%	15%	30%	50%
Probability of Crossing the Safety Boundary	<0.001	0.07	0.71	>.99

### 15.3 Data Analysis

Tables will be created to summarize the toxicities and side effects by organ system, attribution and severity for all participants that receive at least one dose of neratinib.

Rates and associated 95% exact Clopper and Pearson binomial confidence limits will be estimated for 1) grade 2 or higher toxicities attributed to neratinib, 2) all grade GI toxicities (diarrhea, nausea and vomiting), 3) dose reductions, holds and hospitalizations, and 4) the objective response (CR+PR) and clinical benefit (CR+PR+SD) and 5) 16 week progression free survival(PFS). EFS, PFS and OS will be estimated using the product limit method of Kaplan and Meier. Descriptive statistics will be provided for drug adherence and participant demographics. Serum samples from this study will be integrated into a population PK analysis dataset to explore the effects of age on PK parameters (clearance and volume of distribution) and exposure-response relationships on efficacy and safety of neratinib. Generalized linear models and graphical methods will be used to explore factors as identified by a cancer-specific geriatric assessment and serum biomarkers that may be predictive of toxicity dose reductions, dose holds or hospitalizations. We will use generalized linear models to determine if any of these factors independently predict toxicity, response, and/or pharmacokinetic parameters of interest.

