## Experimental Design Schema

	Pre-Study (up to 28 days prior to enrolling) i	Cycle 1 Day 1 (28 day cycle)	Cycle 1 Day 8 (± 1 day)	Cycle 1 Day 15 (± 1 day)	Cycle 2 Day 1 (± 3 days)	Cycle 2 Day 15 (± 3 days)	Cycle 3 Day 1 (± 3 days)	Cycle 4 Day 1 (± 3 days)	Cycle 5 Day 1 (±3 days)	Cycle 6 Day 1 (±3 days)	Every Cycle Thereafter (± 3 days)	Every 3 cycles (±7 days)	Off treatment h
Neratinib (day 1-28 every 4 weeks a,b )		X	X	X	X	X	X	X	X	X	X		
Demographics	X												
Medical history	X												
Concurrent meds (± 1 wk)	X	X			X		X	X	X	X	X		X
Physical exam (± 1 wk)	X	X			X		X	X	X	X	X		X
Vital signs (± 1 wk)	X	X			X		X	X	X	X	X		X
Height	X												
Weight (± 1 wk)	X	X	X	X	X	X	X	X	X	X	X		X
Performance Status (± 1 wk)	X	X			X		X	X	X	X	X		X
CBC w/diff, plts (± 1 wk)	X	X			X		X	X	X	X	X		X
Complete Metabolic Panel c (± 1 wk)	X	X	X	X	X	X	X	X	X	X	X		X
Diarrhea Checklist		X l											
Nurse brief toxicity evaluation		X	X	X	X	X	X						
EKG	X												
Pharmacokinetic samples j				X			X	X					
Adherence evaluation (pill count, diaries) (± 1 wk)		X	X	X	X	X	X	X	X	X	X		
Adverse event evaluation (± 1wk)		X	X	X	X	X	X	X	X	X	X		X
Tumor measurements using CT or PET-CT (± 1 wk)	X d							X				X e	X f
LVEF Assessment	X d							X e				X e	X f

Geriatric Assessment Survey( $\pm 1$ wk) k	X						X					X g
Peripheral Blood Correlatives k	X						X					X
Bacteriomic profiling	X m			X	X	X	X					

a: Dose as assigned; neratinib 240mg orally daily; Doses held due to toxicity will not be made up.

b: If baseline laboratory tests are done within 14 days of start of treatment, these labs do not need to be repeated prior to Day 1.

c: Albumin, alkaline phosphatase, total bilirubin, bicarbonate, BUN, calcium, chloride, creatinine, glucose, potassium, total protein, SGOT[AST], SGPT[ALT], sodium.

d: Baseline assessment may be done up to 30 days prior to study enrollment.

e: Tumor measurements and LVEF assessment are repeated every 3 cycles  $\pm 1$  wk until patient comes off study. Documentation (radiologic or clinical) must be provided for patients removed from study for progressive disease.

f: Off-study radiologic evaluation will only be done if clinically indicated.

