### **7.7.2 Studies Obtained During the Trial**

#### ***7.7.2.1 Disease evaluation***

CT scans of the chest, abdomen, and pelvis; or PET-CT with a diagnostic CT component must be performed every 12 weeks ( $\pm 1$  week) in the absence of symptoms to document disease response or progression. In the presence of symptoms, these tests may be performed at the discretion of the treating physician.

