## **8.0 Dose Delays/Modifications for Adverse Events**

---

Patients will be treated per protocol or until disease progression or withdrawal from treatment due to unacceptable adverse events or treatment consent withdrawal. At each study assessment, subjects are to be evaluated for evidence of drug-related adverse events.

In all cases where the subject is withdrawn due to unusual or unusually severe adverse event considered related to neratinib, the Investigator must report the withdrawal as a Serious Adverse Event.

Treatment may be delayed for up to 4 weeks, to allow for resolution of toxicity except in the event of those toxicities described below in which cases treatment must be discontinued permanently (see **Table 7**).

Recommended dose reductions for the -1 and -2 dose levels of Neratinib are listed as following:

Dose level	Neratinib
Starting dose	240mg
-1	160mg
-2	120mg

If a dose of neratinib is held, study procedures for that cycle will proceed on schedule as planned, without any delay. This also applies to tumor assessments, which should continue to be done every 12 weeks, starting from the first dose of neratinib until the first planned tumor assessment at 12 weeks ( $\pm 1$  wk), and then after every subsequent 12 weeks ( $\pm 1$  week) of treatment regardless of any changes in dose or occurrence of AEs. Missed dose(s) of neratinib (i.e., any

dose that is not administered within the protocol-defined administration window) will not be made up. The dose adjustment guidelines represent the minimum set of measures that investigators must follow. However, additional measures may be taken as necessary, for certain patients per the Investigator's medical judgment. All dose modifications/adjustments should be documented in the patient's source file.

Once neratinib dose has been reduced for a patient, all subsequent cycles must be administered at that dose, unless further dose reduction is required. Dose re-escalation is not permitted.

If a patient developed AE requiring dose reduction while on neratinib dose level of 120mg, neratinib will be discontinued.

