## 12.0 Experimental Design Schema

	Pre-Study (up to 28 days prior to enrolling) i	Cycle 1 Day 1 (28 day cycle)	Cycle 1 Day 8 (± 1 day)	Cycle 1 Day 15 (± 1 day)	Cycle 2 Day 1 (± 3 days)	Cycle 2 Day 15 (± 3 days)	Cycle 3 Day 1 (± 3 days)	Cycle 4 Day 1 (± 3 days)	Cycle 5 Day 1 (± 3 days)	Cycle 6 Day 1 (± 3 days)	Every Cycle Thereafter (± 3 days)	Every 3 cycles (± 7 days)	Off Treatment h
Neratinib (day 1-7 of each wk) a,b		X	X	X	X	X	X	X	X	X	X		
Demographics	X												
Medical history	X												
Concurrent meds (± 1 wk)	X	X			X		X	X	X	X	X		X
Physical exam (± 1 wk)	X	X			X		X	X	X	X	X		X
Vital signs (± 1 wk)	X	X			X		X	X	X	X	X		X
Height	X												
Weight (± 1 wk)	X	X	X	X	X	X	X	X	X	X	X		X
Performance Status (± 1 wk)	X	X			X		X	X	X	X	X		X
CBC w/diff, plts (± 1 wk)	X	X			X		X	X	X	X	X		X
Complete Metabolic Panel c (± 1 wk)	X	X	X	X	X	X	X	X	X	X	X		X
Diarrhea Checklist		X l											
Nurse brief toxicity evaluation		X	X	X	X	X	X						
EKG	X												
Pharmacokinetic samples j				X			X	X					
Adherence evaluation (pill count, diaries) (± 1 wk)		X	X	X	X	X	X	X	X	X	X		
Adverse event evaluation (± 1 wk)		X	X	X	X	X	X	X	X	X	X		X
Tumor measurements using CT or PET-CT (± 1 wk)	X d							X				X e	X f
LVEF Assessment	X d							X e				X e	X f
Geriatric Assessment Survey(±1 wk) k	X							X					X g
Peripheral Blood Correlatives k	X							X					X
Bacteriomic profiling	X m			X	X	X	X						

---

- a: Dose as assigned; neratinib 240mg orally daily; Doses held due to toxicity will not be made up.
- b: If baseline laboratory tests are done within 14 days of start of treatment, these labs do not need to be repeated prior to Day 1.
- c: Albumin, alkaline phosphatase, total bilirubin, bicarbonate, BUN, calcium, chloride, creatinine, glucose, potassium, total protein, SGOT[AST], SGPT[ALT], sodium.
- d: Baseline assessment may be done up to 30 days prior to study enrollment.
- e: Tumor measurements and LVEF assessment are repeated every 3 months  $\pm$  1 wk until patient comes off study. Documentation (radiologic or clinical) must be provided for patients removed from study for progressive disease.
- f: Off-study radiologic evaluation will only be done if clinically indicated.

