### **13.1 Response Criteria**

For the purposes of this study, patients should be reevaluated for response every 12 weeks. Response and progression will be evaluated in this study using the new updated international criteria proposed by the Response Evaluation Criteria in Solid Tumors (RECIST) Committee version 1.1. Per the RECIST criteria, as disease response is not the primary endpoint of this trial, confirmatory scans following documentation of progression or response will not be required. Rather, progression/response will be determined based on results of the single scan.

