### **13.7 Progression-free Survival**

Progression-free survival is determined programmatically from adjudicated PD, defined as the interval from the start of treatment until the first date on which recurrence, progression (per RECIST v1.1) or death due to any cause, is documented, censored at the last assessable evaluation, or at the initiation of new anticancer therapy. It is not necessary to confirm disease progression.

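### 16-week PFS is planned as a binomial proportion, which cannot represent patients censored before week 16; it should be read from the Kaplan-Meier curve already planned

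*Combined protocol and SAP*

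**What the plan says.** Section 15.3 (Data Analysis), repeated in the synopsis under Statistical Considerations, gives a numbered list of rates to be reported with exact Clopper-Pearson 95% limits. The last item is "and 5) 16 week progression free survival(PFS". The sentence after the list states that "EFS, PFS and OS will be estimated using the product limit method of Kaplan and Meier". No landmark time is named for the curve.

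Section 13.7 runs PFS from the start of treatment to documented progression or death, "censored at the last assessable evaluation, or at the initiation of new anticancer therapy". It supplies a censoring date but no week-16 status. The evaluability definition in Section 13.1 covers objective response only, so no denominator is given for 16-week PFS.

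On timing, Section 13.1 says "patients should be reevaluated for response every 12 weeks" and Section 8.0 says of dose holds: "This also applies to tumor assessments, which should continue to be done every 12 weeks, starting from the first dose of neratinib". Section 7.7.2.1 gives a window of ±1 week and adds: "In the presence of symptoms, these tests may be performed at the discretion of the treating physician".

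Footnote e of the schema at the front of the protocol reads "Tumor measurements and LVEF assessment are repeated every 3 cycles". Footnote e of the Section 12.0 schema reads "Tumor measurements and LVEF assessment are repeated every 3 months".

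**The concern.** One quantity has two estimators, and one of them cannot hold the plan's own censoring. A binomial rate requires a fixed denominator and a known status for each patient. A patient who withdraws, or starts another therapy without documented progression, before week 16 has no such status. Whoever runs the analysis must count that patient as a failure, as progression-free, or not at all, and the plan does not choose.

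The stake is modest. The figure would depend on an unstated rule, and readers will probably set it beside the 59% 16-week PFS that Section 1.4.6.1 reports for patients with prior trastuzumab. A few points could colour that comparison. Separately, week 16 falls about four weeks after the first scheduled scan and eight before the second, so the figure needs a note on what it measures.

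**Working it through.** **Inputs from the documents.** N = 40 (Section 15.1). Scans every 12 weeks ±1 (Sections 7.7.2.1, 8.0, 13.1). For illustration, median PFS of 22.3 weeks and 16-week PFS of 59% in the prior-trastuzumab cohort (Section 1.4.6.1).

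**Assumptions, not in the documents.** Exponential PFS, S(t) = 0.5^(t/median). Half of progressions are documented when they occur and the rest at the next scan. 5%, 10% or 15% of patients leave follow-up evenly over weeks 0 to 16, independently of progression, and are censored at their last scan.

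**Step 1: the plan's own binomial figure.** Clopper-Pearson for 8/40 gives 0.0905 to 0.3565, matching the .09 and .36 in Section 15.1. The plan states no figure for 16-week PFS.

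**Step 2: the counting rule by hand.** Suppose 4 of 40 are censored before week 16 and 22 are known to be progression-free.

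- Censored as failures: 22/40 = 55% (95% limits 38% to 71%).
- Censored excluded: 22/36 = 61% (43% to 77%).
- Censored as progression-free: 26/40 = 65% (48% to 79%).

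The gap between the two extreme rules is c/40 for c censored: 5, 10 or 15 points for c = 2, 4 or 6.

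**Step 3: average behaviour.** Simulation of 5,000 trials of 40 patients, median 22.3 weeks:

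| Leaving by week 16 | Full follow-up | As failures | Excluded | As progression-free | Kaplan-Meier |
|---|---|---|---|---|---|
| 5% | 64.9% | 61.6% | 64.4% | 65.9% | 64.6% |
| 10% (mean 3.4 censored) | 64.8% | 58.3% | 63.8% | 66.9% | 64.2% |
| 15% | 65.0% | 55.2% | 63.4% | 68.1% | 63.9% |

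At 10%, Kaplan-Meier is 0.6 points below full follow-up (64.8 − 64.2), against 6.5 below for failures and 2.1 above for progression-free. Its gain over exclusion is only 0.2, 0.4 and 0.5 points in the three rows. The reason is the censoring date: a patient lost before the week-12 scan has no later assessable evaluation, so is censored at baseline and leaves the risk set at time zero. About 80% of the censored patients in the 10% scenario are of this kind. With continuous assessment the gap would be wider (57.7% excluded against 59.1% by Kaplan-Meier, at a true 59% and a 10% chance of censoring by week 16), but that is not this trial's schedule.

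**Step 4: scan timing.** S(16) = 0.5^(16/22.3) = 60.8%. If no progression were found between scans, the week-16 reading would be the mean of S over weeks 11 to 13, which is 68.9%. The shift is 68.9 − 60.8 = 8.1 points, an upper bound. If half of events are documented off schedule it is 8.1 × 0.5 = 4.0 points. The estimator makes no difference: at a true 59% with nobody censored, the proportion and Kaplan-Meier at week 16 both read 67.8%, 65.3% or 62.6% when 0%, 30% or 60% of progressions are found at once. Kaplan-Meier read just after a scan window leaves at most 68.9 − 66.8 = 2.1 points at week 13, and at most 1.5 points at week 25.

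**The case against.** The best reply is that this is a missing sentence about the denominator, not a wrong method. A proportion among evaluable patients is within 0.5 points of Kaplan-Meier in every row above. Kaplan-Meier is planned anyway, and 16 weeks matches the primary endpoint of the earlier single-agent study. Kaplan-Meier also assumes that censoring carries no information, which is doubtful for patients who stop for toxicity or start new therapy. Section 13.5.1 asks for progression to be documented after treatment stops, and Section 7.7.3.4 traces deaths, so few patients may be censored. With none censored, the methods agree.

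Much of this stands, and it limits the size of the point. It does not supply the missing rule, and the plan's own curve removes the need to invent one.

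A reader might infer three stronger things that the documents do not support:

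- **That the binomial plan costs 5 to 15 points.** That is the distance between two extreme counting rules under assumed numbers censored, not the distance from a reasonable proportion to Kaplan-Meier.
- **That the 16-week rate will read high.** The 8.1 points assume no symptom-driven scans, which Section 7.7.2.1 allows. The direction also depends on the counting rule: with censored patients as failures the averages at 10% and 15% are 58.3% and 55.2%, below the 60.8% true rate. Section 13.7 counts documented progression, so the reading is not misclassification, and Kaplan-Meier at week 16 shares it.
- **That the scan schedule is in real conflict.** The 12-week interval, or three 28-day cycles, appears in the synopsis, Sections 7.7.2.1, 8.0 and 13.1, the front schema and Appendix R. Only footnote e in Section 12.0 says 3 months, under a table whose own column is headed in cycles.

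**Conclusion.** The point holds as a minor one. A binomial proportion cannot represent the censoring in Section 13.7, and reading the 16-week figure from the planned Kaplan-Meier curve is the better method. With an assumed 10% leaving by week 16, the unstated rule moves the average from about 58% to about 67%, while Kaplan-Meier stays within 1 point of full follow-up. Against a proportion among evaluable patients, the gain is under 1 point. The timing of week 16 between scans is a matter of interpretation to be stated; the change of estimator does not correct it.

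These sizes rest on the assumed dropout, curve shape and detection share, on independent dropout, and on taking the earlier study's median as a true progression time. Sampling error is larger than any of these shifts: 26/40 has exact limits of 48% to 79%. The rate is descriptive, and 16-week PFS is not itself listed as an endpoint in Section 3.2 or the synopsis.

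**What to change.** - In Section 15.3 and the synopsis, remove item 5 from the Clopper-Pearson list. Report 16-week PFS with 95% limits from the planned Kaplan-Meier curve.
- State that this assumes uninformative censoring, and that stopping for toxicity or starting new therapy may break the assumption. Add a sensitivity count with patients censored before week 16 as failures, and report how many there were.
- State that week 16 lies between the scheduled scans and that Kaplan-Meier does not remove this.
- Optionally, also report Kaplan-Meier PFS just after the first and second scan windows (about weeks 13 and 25). Before fixing those times, reconcile footnote e in Section 12.0 with the 12-week, 3-cycle wording elsewhere.

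The cost is analysis wording only: no extra scans, data or patients. Keeping week 16 preserves the comparison with the earlier study; moving the landmark would make that match slightly less direct.
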